10.4 Prior and Concomitant Medications

Verbatim terms on case report forms will be mapped to Anatomical/Therapeutic/Chemical (ATC) Level 4 categories and Drug Reference Names using the World Health Organization (WHO) dictionary (March 1, 2009).

Prior medications are those medications taken within 21 days prior to the initial dose of study drug. Concomitant medications are those medications taken after the initial dose of study drug. Prior and concomitant medications will be summarized for each treatment by WHO ATC class and medication name. These summaries will present the number and percentage of subjects using each medication. Subjects may have more than one medication per ATC category and medication. At each level of subject summarization, a subject is counted once if he/she reported one or more medications at that level. Each summary will be ordered by descending order of incidence of ATC class and medication within each ATC class.

11. SAMPLE SIZE CALCULATION

The sample size of 20 evaluable subjects is intended to provide a sufficient sample size to allow for a meaningful comparison between rHuPH20 and placebo control.

APPENDIX A: LIST OF TABLES, LISTINGS AND FIGURES

List of Tables

Table Number	Table Description
1	Subject Disposition
2	Demographic and Baseline Characteristics
3	Abnormal Medical History
4	Hematology and CBC with Differential at Screening
5	Incidence of Clinically Significant Laboratory Abnormalities at Screening
6	Day of Maximal ICDRG Score
7	Adverse Events by System Organ Class (Safety Population)
8	Adverse Events by System Organ Class and Severity [1] (Safety Population)
9	Adverse Events by System Organ Class and Relationship to Study Drug [1] (Safety Population)
10	Serious Adverse Events by System Organ Class (Safety Population)
11	Adverse Events Leading to Discontinuation of Study Drug or Premature Withdrawal of From Study
12	Adverse Events by System Organ Class and Injection Type (Safety Population)
13	Vital Signs (Safety Population)
14	Physical Examination (Safety Population)
15	Concomitant Medications (Safety Population)

List of Data Listings

Listing Number	Listing Description	CRF Plate(s)
1	Subject Disposition	Derived
2	Inclusion/Exclusion Criteria	2,3,4
3	Demographics	1
4	Medical History	5
5	Hematology and CBC with Differential	8
6	Lab Normal - Hematology	350
7	Pregnancy Test	9
8	ICDRG Score	13,15
9	TEWL (Trans-Epidermal Water Loss) Assessment	17
10	Digital Photographs	17
11	Chromometer	18
12	Subject Diary	19
13	Screening Nickel Sulfate and Vehicle Control Patches	11
14	Study Drug Administration – Treatment Regimen 1	12,13,14
15	Study Drug Administration – Treatment Regimen 2	15,16
16	Adverse Events	97
17	Serious Adverse Events	97
18	Vital Signs	7
19	Physical Examination	6,10
20	Comments	96
21	Prior and Concomitant Medications	98
22	Deaths	101
23	Subject Visit	Derived

List of Figures

Figure Number	Figure Description
1	ICDRG Scores by Day
2	Individual TEWL Scores by Day and Injection Site
3	Individual a-Scale Chromometer Baseline Corrected Scores by Day and Injection Site

APPENDIX B: TABLE LAYOUTS

Table 1
Subject Disposition
All Subjects

	Total
ITT Population[1]	N
Safety Population [2]	n (%)
Evaluable Population [3]	n (%)
Number of Subjects Replaced [4]	n (%)
Completed Study	
Yes	n (%)
No	n (%)
Primary Reason for Discontinuation	
Protocol Violation	n (%)
Lost to Follow-up	n (%)
Adverse Event	n (%)
Non-compliance	n (%)
Subject Decision	n (%)
Investigator Decision	n (%)
Other	n (%)

[1] Intent to Treat (ITT): Enrolled subjects who signed informed consent.

[2] Received at least one dose of study drug.

[3] An evaluable subject is one who has completed dosing (or prematurely discontinued the administration due to a toxicity) and has undergone sufficient assessments to allow an assessment of the tolerability of the administration.

[4] Enrolled subjects but not meeting the criteria of evaluability.

path\t_program.sas date time

Table 2
Demographic and Baseline Characteristics
All Subjects

	ITT (N=)	Safety (N=)	Evaluable (N=)
Age (years) [1]			
N	n	n	n
Mean (SD)	xx.x (xx.xx)	xx.x (xx.xx)	xx.x (xx.xx)
Median	xx.x	xx.x	xx.x
Min, Max	xx, xx	xx, xx	xx, xx
Sex			
Male	n (%)	n (%)	n (%)
Female	n (%)	n (%)	n (%)
Ethnicity			
Hispanic or Latino	n (%)	n (%)	n (%)
Not Hispanic or Latino	n (%)	n (%)	n (%)
Race			
American Indian or Alaska Native	n (%)	n (%)	n (%)
Asian	n (%)	n (%)	n (%)
Black or African American	n (%)	n (%)	n (%)
Native Hawaiian or Other Pacific Islander	n (%)	n (%)	n (%)
White	n (%)	n (%)	n (%)
Other	n (%)	n (%)	n (%)
More than one race marked	n (%)	n (%)	n (%)
Concentration of nickel sulfate (%)			
1	n (%)	n (%)	n (%)
2.5	n (%)	n (%)	n (%)
5	n (%)	n (%)	n (%)

[1] Age at the date of informed consent signed.
path\t_program.sas date time

Table
Abnormal Medical History
All Subjects

Body System	ITT (N=)	Safety (N=)	Evaluable (N=)
Respiratory	n (%)	n (%)	n (%)
Cardiovascular	n (%)	n (%)	n (%)
Gastrointestinal	n (%)	n (%)	n (%)
Hepatic	n (%)	n (%)	n (%)
Endocrine/Metabolic	n (%)	n (%)	n (%)
Central and Peripheral Nervous System	n (%)	n (%)	n (%)
Hematopoietic/Lymphatic	n (%)	n (%)	n (%)
Dermatological	n (%)	n (%)	n (%)
Musculoskeletal	n (%)	n (%)	n (%)
Genitourinary/Reproductive	n (%)	n (%)	n (%)
Psychiatric	n (%)	n (%)	n (%)
Alcohol/Drug Abuse	n (%)	n (%)	n (%)
Drug Allergy	n (%)	n (%)	n (%)
Non-Drug Allergy	n (%)	n (%)	n (%)
HEENT	n (%)	n (%)	n (%)
Other	n (%)	n (%)	n (%)

path\t_program.sas date time

Table
Hematology and CBC with Differential at Screening
All Subjects

Laboratory Parameter	ITT (N=)	Safety (N=)	Evaluable (N=)
WBC (X 1000/uL)			
N	n	n	n
Mean (SD)	xx.x (xx.xx)	xx.x (xx.xx)	xx.x (xx.xx)
Median	xx.x	xx.x	xx.x
Min, Max	xx, xx	xx, xx	xx, xx
RBC (X Mil/uL)			
N	n	n	n
Mean (SD)	xx.x (xx.xx)	xx.x (xx.xx)	xx.x (xx.xx)
Median	xx.x	xx.x	xx.x
Min, Max	xx, xx	xx, xx	xx, xx
..			

path\t_program.sas date time

Programmer note: Table will include the following hematology parameters: Hemoglobin (g/dL), Hematocrit (%), Platelets (X 1000/uL), Neutrophils (segs) (%), Neutrophils (bands) (%), Lymphocytes (%), Monocytes (%), Eosinophils (%) and Basophils (%).

Table
Incidence of Clinically Significant Laboratory Abnormalities at Screening
All Subjects

Any Clinically Significant Abnormalities?	ITT (N=)	Safety (N=)	Evaluable (N=)
WBC	n (%)	n (%)	n (%)
RBC	n (%)	n (%)	n (%)
Hemoglobin	n (%)	n (%)	n (%)
Hematocrit	n (%)	n (%)	n (%)
Platelets	n (%)	n (%)	n (%)
Neutrophils (segs)	n (%)	n (%)	n (%)
Neutrophils (bands)	n (%)	n (%)	n (%)
Lymphocytes	n (%)	n (%)	n (%)
Monocytes	n (%)	n (%)	n (%)
Eosinophils	n (%)	n (%)	n (%)
Basophils	n (%)	n (%)	n (%)

path\t_program.sas date time

Table 6.1
Day of Maximal ICDRG Score
Evaluable Population

Day of ICDRG Maximal Severity Score	Treatment Regimen 2 (N=)	
	rHuPH20	Placebo
Never had an ICDRG Score More Severe than Day 3	n (%)	n (%)
Day 4	n (%)	n (%)
Day 5	n (%)	n (%)
Day 6	n (%)	n (%)
Day 7	n (%)	n (%)
Day 14	n (%)	n (%)

Note: For both injection types (rHuPH20 and Placebo), each subject will contribute one result based on the single most severe patch assessment reported.
path\t_program.sas date time

Programmer Note: Table 6.2 will contain the same information for the ITT population.

Table
Treatment Emergent Adverse Events by System Organ Class
Safety Population

System Organ Class / Preferred Term	Safety Population (N=)	
	Number of Subjects [1]	Number of Events
Subjects Reporting at Least One Adverse Event	n (%)	n
System Organ Class 1	n (%)	n
Preferred Term 1	n (%)	n
Preferred Term 2	n (%)	n
.		
System Organ Class 2	n (%)	n
Preferred Term 1	n (%)	n
Preferred Term 2	n (%)	n

[1] At each level of summation (overall, system organ class, preferred term), subjects reporting more than one adverse event are counted only once.
path\t_program.sas date time

Table
Treatment Emergent Adverse Events by System Organ Class and Severity
Safety Population

System Organ Class / Preferred Term [1]	Safety Population (N=)				
	Mild	Moderate	Severe	Life Threatening	Fatal
Subjects Reporting at Least One Adverse Event	n (%)	n (%)	n (%)	n (%)	n (%)
System Organ Class 1	n (%)	n (%)	n (%)	n (%)	n (%)
Preferred Term 1	n (%)	n (%)	n (%)	n (%)	n (%)
Preferred Term 2	n (%)	n (%)	n (%)	n (%)	n (%)
.
System Organ Class 2	n (%)	n (%)	n (%)	n (%)	n (%)
Preferred Term 1	n (%)	n (%)	n (%)	n (%)	n (%)
Preferred Term 2	n (%)	n (%)	n (%)	n (%)	n (%)
.

[1] At each level of summation (overall, system organ class, preferred term), subjects reporting more than one adverse event are counted only once using the highest severity.
path\t_program.sas date time

Table
Treatment Emergent Adverse Events by System Organ Class and Relationship to Study Drug
Safety Population

System Organ Class / Preferred Term [1]	Safety Population (N=)	
	Related	Not Related
Subjects Reporting at Least One Adverse Event	n (%)	n (%)
System Organ Class 1	n (%)	n (%)
Preferred Term 1	n (%)	n (%)
Preferred Term 2	n (%)	n (%)
.		
System Organ Class 2	n (%)	n (%)
Preferred Term 1	n (%)	n (%)
Preferred Term 2	n (%)	n (%)

[1] At each level of summation (overall, system organ class, preferred term), subjects reporting more than one adverse event are counted only once using the closest relationship to study drug.
path\t_program.sas date time

Table 28
Treatment Emergent Serious Adverse Events by System Organ Class
Safety Population

System Organ Class / Preferred Term	Safety Population (N=)	
	Number of Subjects [1]	Number of Events
Subjects Reporting at Least One Serious Adverse Event	n (%)	n
System Organ Class 1	n (%)	n
Preferred Term 1	n (%)	n
Preferred Term 2	n (%)	n
.		
System Organ Class 2	n (%)	n
Preferred Term 1	n (%)	n
Preferred Term 2	n (%)	n

[1] At each level of summation (overall, system organ class, preferred term), subjects reporting more than one serious adverse event are counted only once.
path\t_program.sas date time

Table 29
Treatment Emergent Adverse Events Leading to Discontinuation of Study Drug or Premature Withdrawal of From Study Safety Population

System Organ Class / Preferred Term	Safety Population (N=)	
	Number of Subjects [1]	Number of Events
Subjects Reporting at Least One Serious Adverse Event	n (%)	n
System Organ Class 1	n (%)	n
Preferred Term 1	n (%)	n
Preferred Term 2	n (%)	n
.		
System Organ Class 2	n (%)	n
Preferred Term 1	n (%)	n
Preferred Term 2	n (%)	n

[1] At each level of summation (overall, system organ class, preferred term), subjects reporting more than one adverse event are counted only once.
path\t_program.sas date time

Table 12
Treatment Emergent Adverse Events by System Organ Class and Injection Type
Safety Population

System Organ Class / Preferred Term	Treatment Regimen 1 (N=)				Treatment Regimen 2 (N=)			
	rHuPH20		Placebo		rHuPH20		Placebo	
	Number of Subjects [1]	Number of Events	Number of Subjects [1]	Number of Events	Number of Subjects [1]	Number of Events	Number of Subjects [1]	Number of Events
Subjects Reporting at Least One Serious Adverse Event	n (%)	n	n (%)	n	n (%)	n	n (%)	n
System Organ Class 1	n (%)	n	n (%)	n	n (%)	n	n (%)	n
Preferred Term 1	n (%)	n	n (%)	n	n (%)	n	n (%)	n
Preferred Term 2	n (%)	n	n (%)	n	n (%)	n	n (%)	n
.								
System Organ Class 2	n (%)	n	n (%)	n	n (%)	n	n (%)	n
Preferred Term 1	n (%)	n	n (%)	n	n (%)	n	n (%)	n
Preferred Term 2	n (%)	n	n (%)	n	n (%)	n	n (%)	n

Note: For this summary, only Adverse Events reported during the physical examinations/safety reviews at Day 1 (TR 2 only), Day 3 through Day 7, and Day 14 are considered.

[1] At each level of summation (overall, system organ class, preferred term), subjects reporting more than one adverse event are counted only once.

path\t_program.sas date time

Table 31
Vital Signs
Safety Population

Vital Sign	Time Point	Safety Population (N=)
Systolic BP (mmHg)	Screening	
	N	n
	Mean (SD)	xx.x (xx.xx)
	Median	xx.x
	Min, Max	xx, xx
	Day 1 Pre-Injection	
	N	n
	Mean (SD)	xx.x (xx.xx)
	Median	xx.x
	Min, Max	xx, xx
	Day 1 Post-Injection	
	N	n
	Mean (SD)	xx.x (xx.xx)
	Median	xx.x
	Min, Max	xx, xx
	Day 1 Change from Baseline [1]	
	N	n
	Mean (SD)	xx.x (xx.xx)
	Median	xx.x
	Min, Max	xx, xx
	...	
Diastolic BP (mmHg)		

[1] Baseline is defined as pre-injection assessment for the visit under consideration.
path\t_program.sas date time

Programmer note: Table will include the following vital signs: systolic BP (mmHg), diastolic BP (mmHg), Heart Rate (bpm) and Respiration (breaths/min). for each vital sign, time points will include: Screening, Day 1 Pre-Injection, Day 1 Post-Injection, Day 1 Change from Baseline, Day 3 Pre-Injection, Day 3 Post-Injection, Day 3 Change from Baseline, Day 4 Pre-Injection, Day 4 Post-Injection, Day 4 Change from Baseline, Day 5 Pre-Injection, Day 5 Post-Injection, Day 5 Change from Baseline, Day 6 Pre-Injection, Day 6 Post-Injection, Day 6 Change from Baseline, Day 7 Pre-Injection, Day 7 Post-Injection, Day 7 Change from Baseline, Day 14.

Table 32
Physical Examination
Safety Population

Most Abnormal Post-Baseline Assessment	Safety Population (N=)	
	Normal	Abnormal
HEENT		
Normal	(N=) n (%)	n (%)
Abnormal	n (%)	n (%)
Respiratory		
Normal	(N=) n (%)	n (%)
Abnormal	n (%)	n (%)
Cardiovascular		
.		

path\t_program.sas date time

Programmer note: Table will include all physical examination body systems.

Table 15
Concomitant Medications [1]
Safety Population

ATC Drug Class / Medication Term	Safety Population (N=)
Subjects Receiving any Concomitant Medications	n (%)
Drug Class 1	n (%)
Medication Term 1	n (%)
Medication Term 2	n (%)
.	.
Drug Class 2	n (%)
Medication Term 1	n (%)
Medication Term 2	n (%)
.	.

[1] At each level of summation (overall, ATC drug class, medication term), subjects reporting more than one medication are counted only once.
path\t_program.sas date time

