### Dataset for Analysis

The primary analysis data set for this study will consist of all evaluable subjects. An evaluable subject is one who has completed dosing (or prematurely discontinued the administration due to a toxicity) and has undergone sufficient assessments to allow an assessment of the tolerability of the administration. A secondary analysis data set will consist of all intent-to treat subjects (ITT) (i.e., all subjects enrolled, defined as subjects assigned a subject identification number at the time of study enrollment in anticipation of receiving a dose of study drug). The safety analysis data set is all subjects exposed to rHuPH20 or placebo control.

The hypothesis is that 1) pre-treatment of rHuPH20 prior to nickel allergy testing will decrease the severity of the allergic skin reaction as compared to placebo control and 2) rHuPH20 will decrease the severity of nickel contact dermatitis as compared to control. The null hypothesis for this study is that rHuPH20 will not be different than what will be observed from placebo control. The alternative hypothesis is that rHuPH20 will be better than placebo control.

The sample size of 20 evaluable subjects is intended to provide a sufficient sample size to allow for a meaningful comparison between rHuPH20 and placebo control.

All data collected, including demographics, baseline information, contact dermatitis scoring, safety data, will be summarized by treatment group. Descriptive statistics including the number of observations (N), mean, standard deviation, median, and range will be presented for the continuous variables. Frequency and percentage will be presented for categorical variables. Figures of the individual measurements over time by subject and means by treatment group may also be provided.

Descriptive statistics will be used to summarize all efficacy variables. No formal statistical comparisons between treatments are planned.

All safety data will be examined, including AEs, physical examination findings, and vital signs. The incidence of subjects with AEs will be tabulated by MedDRA System Organ Class (SOC) and Preferred Term, seriousness, severity grade, relatedness to study drug, and localization to infusion site. Descriptive statistics will be used to summarize all safety variables.

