10.1 Adverse Events

All adverse event summaries will be restricted to Treatment Emergent Adverse Events (TEAE), which are defined as those AEs that occurred after dosing and those existing AEs that worsened during the study. Verbatim terms on case report forms will be mapped to preferred terms and system organ classes using the MedDRA dictionary (version 12.0).

Each adverse event summary will be displayed for the Safety population. Summaries that are displayed by system organ class and preferred terms will be ordered by descending order of incidence of system organ class and preferred term within each system organ class. Summaries of the following types will be presented:

- Subject incidence of TEAEs and total number of unique TEAEs by MedDRA system organ class and preferred term.
- Subject incidence of TEAEs by MedDRA system organ class, preferred term, and highest severity. At each level of subject summarization a subject is classified according to the highest severity if the subject reported one or more events. A

missing column will be added to the summary table if any TEAEs are reported with missing severity.

- Subject incidence of TEAEs by MedDRA system organ class, preferred term, and closest relationship to study drug (Related/Not Related). At each level of subject summarization a subject is classified according to the closest relationship if the subject reported one or more events. AEs with a missing relationship will be considered related for this summary.
- Subject incidence of serious TEAEs and total number of unique serious TEAEs by MedDRA system organ class and preferred term.
- Subject incidence of TEAEs and total number of unique serious TEAEs leading to discontinuation of study drug or premature withdrawal from study.
- Subject incidence of TEAEs reported after physical examination of injection site and safety review on Day 1 (for Treatment Regimen 2 only), Day 3 through Day 7 and Day 14 will be presented by injection type.

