TEWL (Trans-Epidermal Water Loss) Assessment (g/m²h)

Subject	Visit	Was TEWL Completed?	Collection Date/Time	Result							
				TR 1-1	TR 1-2	TR 1-3	TR 1-4	TR 2-5	TR 2-6	TR 2-7	TR 2-8
	Day 1										
	Day 3										
	..										

path\t_program.sas date time

Listing 45
Digital Photographs

Subject	Visit	Were Digital Photos Taken?	Collection Date	Collection Time	Uploaded to Website?
		No:reason			No:reason

path\t_program.sas date time

Listing 46
Chromometer
Part 1 of 3: a-Scale

Subject	Visit	Was a Chromometer Reading Completed?	Collection Date	Collection Time	Category	TR 1-1	TR 1-2	TR 1-3	TR 1-4	TR 2-5	TR 2-6	TR 2-7	TR 2-8
	Day 1	No:reason											
	Day 3				Result Change from Day 1								

path\t_program.sas date time

Listing 11
Chromometer
Part 2 of 3: b-Scale

Subject	Visit	Was a Chromometer Reading Completed?	Collection Date	Collection Time	Category	TR 1-1	TR 1-2	TR 1-3	TR 1-4	TR 2-5	TR 2-6	TR 2-7	TR 2-8
	Day 1	No:reason											
	Day 3				Result Change from Day 1								

path\t_program.sas date time

Listing 11
Chromometer
Part 3 of 3: l-Scale

Subject	Visit	Was a Chromometer Reading Completed?	Collection Date	Collection Time	Category	TR 1-1	TR 1-2	TR 1-3	TR 1-4	TR 2-5	TR 2-6	TR 2-7	TR 2-8
	Day 1	No:reason											
	Day 3				Result Change from Day 1								

path\t_program.sas date time

Listing 47
Subject Diary

Subject	Visit	Mark if Not Done	Not Done Reason	Date	Start Time	End Time	Symptom	Severity[1]	Comments	Dispense next Diary to subject?
						ongoing				

[1] 1 – Least Discomfort, 5 – Most Discomfort.

path\t_program.sas date time

Listing 48
Screening Nickel Sulfate and Vehicle Control Patches

Subject	Application of Patches				Test Results (48 Hours After Application)						
	Patches Applied?	Date	Time	Date	Time	48 hours After App.?	ICDRG			Dose Assigned?	Assigned Dose
No:reason				No:reason				No:reason			No:reason
path\t_program.sas	date	time					1%	2.5%	5%		

Listing 49
Study Drug Administration – Treatment Regimen 1
Part 1 of 4: Application of Nickel Sulfate Patches

Subject	Visit	Treatment Date	8 Areas Normal?	Application Time	4 Patches applied?	Concentrations of Nickel Sulfate
No:reason						

path\t_program.sas date time

Listing 14 (cont.)
Study Drug Administration – Treatment Regimen 1
Part 2 of 4: Physical Examination Prior to Injection

Subject	Visit	Subject Randomized?	Treatment Date	Asse. Time	ICDRG Score				AE #			

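### Table 12, the only SAP summary table that splits safety by injection type, gives no severity, labels its overall row as serious events, and omits site events not reported at a listed review

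*SAP*

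**What the plan says.** Both documents list safety and tolerability of the injection among the primary objectives (Protocol 2.1, SAP 2). Protocol section 8 makes the rHuPH20 versus placebo comparison of safety part of the secondary analysis. It states that the collected data, safety data included, "will be summarized by treatment group". It names seriousness, severity grade, relatedness and localization among the items for tabulating AEs.

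SAP 10.1 lists six AE summaries. Five are for the whole Safety population, including the one by highest severity. The sixth is by injection type and reads: "Subject incidence of TEAEs reported after physical examination of injection site and safety review on Day 1 (for Treatment Regimen 2 only", continuing to Days 3 to 7 and Day 14.

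In SAP Appendix B, the Table 12 shell is headed "Treatment Emergent Adverse Events by System Organ Class and Injection Type". It has columns for subjects and events under each injection type within each regimen, and none for severity. Its note restricts it to "only Adverse Events reported during the physical examinations/safety reviews" on the listed days. Its overall row is "Subjects Reporting at Least One Serious Adverse Event", while its footnote says "subjects reporting more than one adverse event are counted only once".

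For discontinuations, SAP 10.1 asks for the subject incidence of TEAEs together with the "total number of unique serious TEAEs leading to discontinuation of study drug or premature withdrawal from study". The matching shell (Table 11 in the list of tables, headed Table 29 in the layouts) has the same serious-event overall row as Table 12.

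**The concern.** Each subject receives both injection types, so a systemic AE cannot be assigned to one of them. A reaction at an injection site can. Local tolerability is therefore the safety question this within-subject design is able to answer, and Table 12 is where the SAP answers it. No formal comparisons are planned, so the tables are the result and no test stands behind them.

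If Table 12 shows only how many subjects reacted and not how badly, a difference in intensity between active and placebo sites will not appear in any table. If the overall row or the discontinuation event count is programmed as written, the most-read figures could show nothing while the rows beneath show reactions.

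**Working it through.** The plan gives no AE rate and no calculation to reproduce. The check compares the text with the shells and adds a count of days.

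**1. Which tables split safety by injection type.** Tables 7 to 11 (AEs) and 13 to 15 (vital signs, physical examination, concomitant medication) have a single Safety-population block in their shells. Only Table 12 has rHuPH20 and placebo columns.

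**2. Whether severity can be recovered by injection type.**
- The severity table has five severity columns and no injection-type columns. It counts each subject once, at the highest severity.
- Listings 14 and 15 give an AE number per site, but no severity.
- Listing 16 gives CTCAE severity per AE, but its layout has no AE number, site or injection type. The listings as laid out cannot be joined.

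Illustration (assumed figures): in one regimen, 10 of 20 subjects each have one mild reaction at a placebo site and one severe reaction of the same preferred term at an rHuPH20 site.
- Table 12: rHuPH20 10/20 = 50%, 10 events; placebo 10/20 = 50%, 10 events.
- Pooled severity table: severe 10/20 = 50%, mild 0.

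If the two injection types are swapped, both tables stay exactly the same. Neither can show which injection gave the severe reactions.

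**3. The overall row of Table 12.** The title, the footnote and the SAP 10.1 bullet all cover TEAEs in general. Only the row label says serious. The same label is correct in the serious-AE shell (headed Table 28). If no SAE occurs (assumption) and the label is followed, the row reads 0/N = 0% for all four regimen-by-injection groups. In the illustration it would read 0% above a row reading 50%.

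**4. The discontinuation summary.** Here the restriction is in the SAP 10.1 sentence as well as in the row label. In that sentence it qualifies the event count; the subject incidence is of TEAEs. One subject who stops for a non-serious site reaction gives subjects = 1 and events = 0, which is not a coherent row.

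**5. The visit restriction.** Review days are Day 1 (Regimen 2 only), Days 3 to 7 and Day 14.

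| Regimen | First injection to Day 14 | Days with a review | Days without |
|---|---|---|---|
| 1 | Day 3 to 14: 14 − 3 + 1 = 12 | 6 | 12 − 6 = 6 (Days 8–13) |
| 2 | Day 1 to 14: 14 − 1 + 1 = 14 | 7 | 14 − 7 = 7 (Day 2, Days 8–13) |

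Every injection day is a review day. An event that starts on a day without a review still enters Table 12 if it is reported at the next one. What is lost is a site-attributable AE not reported at any listed review, or one reported after Day 14. Protocol 7.7 collects all AEs through Visit 8 and sets no time limit for drug-associated ones, so such events can be in the database and outside the table.

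**The case against.** The strongest reply is that this is a descriptive pilot of about 20 evaluable subjects and that Table 12 already gives subject and event counts by preferred term, injection type and regimen. Protocol section 8 names severity as a tabulation item but does not expressly require it to be crossed with treatment. The overall-row label looks copied from the serious-AE shell, and a careful programmer would notice. These points are fair. They show that incidence can be compared and that the label is probably a slip. They do not supply severity by injection type, and they do not explain the wording of the SAP 10.1 discontinuation bullet.

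Five stronger readings are tempting, and the documents do not support them.

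- *Table 12 catches only what appears within 30 minutes of an injection.* Protocol 5.3.17 requires a site check before each injection as well as 10 minutes after. Listings 14 and 15 carry an AE number per site at the pre-injection examination. Protocol 7.7 has subjects asked about the time since the last visit.
- *Table 12 is by rule a table of serious events.* The restriction in SAP 10.1 sits in the discontinuation bullet, not in the bullet that governs Table 12.
- *Nothing else shows safety by site.* Listings 14 and 15 show AE numbers by site, and Listing 8 and Figure 1 label each site as active or placebo. Table 12 is the only summary table, not the only output.
- *The two injections cannot be compared on tolerability.* They can be compared on incidence. What is missing is severity and a guaranteed complete count.
- *Diary discomfort ("1 – Least Discomfort, 5 – Most Discomfort") cannot be assigned to an injection.* Only the listing shell is available. It has symptom and comment columns, and the diary page itself is not in the documents.

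**Conclusion.** The point holds as a set of specific defects in the safety outputs, and they should be corrected.

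The main one is that no table gives severity by injection type and the listing layouts cannot be joined to recover it. That falls short of a reasonable reading of Protocol section 8 for a primary objective. Its numerical effect cannot be stated, because the documents give no AE rates; the 10-of-20 illustration is an assumption.

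The overall row of Table 12 contradicts its own title, footnote and governing text. Its effect (0% for all four groups) rests on two assumptions: that no SAE occurs and that the label is followed literally. The discontinuation event count is wrong as specified whenever a subject stops for a non-serious event.

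The visit restriction is the least of these. The gap is real but probably small, and the documents do not allow it to be sized.

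**What to change.** Before database lock and unblinding:

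1. Add highest severity by injection type and regimen. Four regimen-by-injection groups times the five severity columns of the existing shell make 4 × 5 = 20 columns, so a companion table, perhaps one per regimen, is more readable than widening Table 12.
2. Change the overall rows of Table 12 and of the discontinuation table to subjects with at least one TEAE.
3. Delete the word serious from the discontinuation bullet in SAP 10.1, so that subjects and events are counted on the same basis.
4. Let Table 12 include every TEAE that can be linked to a site, whenever reported, and make its note and the SAP 10.1 bullet say the same thing. Make the link to a site while still blinded.
5. Add AE number and site or injection type to Listing 16, so that severity can be traced to a site.

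The cost is a few lines of SAP text, two row labels, one extra table and a slightly wider listing. Table 12 already presupposes an AE-to-site link for events found at reviews. If the AE page of the CRF, which is not in the documents, does not record the site for events reported at other times, item 4 also needs one field or a cross-reference there.
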